4 POPULATIONS FOR ANALYSIS

4.1 Modified Intent-to-Treat Population

The modified intent-to-treat (mITT) population will include all randomized subjects who received at least one dose of the study product. All subjects will be analyzed according to the treatment group to which they were randomized. The mITT population will be used as the primary analysis population for efficacy.

4.2 Per-Protocol Population

The per-protocol (PP) population will include all randomized, eligible subjects who received at least one dose of study product, with no major protocol deviations, and who provided evaluable data for the primary efficacy endpoint. All subjects will be analyzed according to the treatment that they actually received.

The protocol deviations will be presented in a listing and summarized by category. Upon sponsor's review, the listing will also include a flag indicating whether each deviation is considered important or not. Important deviations will be interpreted as major and will result in excluding the related subject from the Per Protocol Population. This exercise will be done prior to the database lock, on blinded data.

	STATISTICAL ANALYSIS PLAN, Version Final 2.0
Protocol Number: ASN002AD-201 V3.0	Sponsor: Asana BioSciences, LLC

4.3 Safety Population

The safety population will include all subjects who received at least one dose of the study product. All subjects will be analyzed according to the treatment that they actually received.

4.4 Pharmacokinetic Population

The Pharmacokinetic (PK) population will include all subjects who received at least one dose of ASN002 and have plasma concentration data.

4.5 Pharmacodynamic Population

The Pharmacodynamic (PD) population will include all subjects who have at least one assessments of PD parameters.

5 GENERAL CONSIDERATIONS

Formats and layouts of tables, listings, and figures (TLF) will be provided in a separate document (output general layout is described in [Appendix 1](#)).

5.1 Sample Size

Using the following assumptions for the primary efficacy endpoint: a change-from-baseline in EASI at week 12 of at least -15 in the ASN002 dosing groups, a change-from-baseline of -8 in the placebo group, a common standard-deviation of 8, nominal alpha of 0.0167 for each comparison of interest, we would need 40 evaluable subjects per group in order to achieve a power of 92% on the primary efficacy endpoint.

Moreover, with 46 subjects per group, we would have 80% power to show a statistically significant difference between the higher dosing group and placebo in IGA responses (one of the key secondary efficacy endpoint), assuming a response of 37.5% vs. 11.1% in the higher dosing and placebo groups, respectively, using an alpha of 5%.

Thus, assuming about 15% dropout rate, 55 subjects per group will need to be enrolled in this trial for a total of 220 subjects in order to have a minimum of 46 subjects per group to evaluate efficacy with adequate power.

5.2 Baseline

Unless otherwise specified, baseline value will be defined as the last nonmissing assessment prior to or on the first study treatment dose (including unscheduled assessments). If the last nonmissing assessment is performed on the same date as the first study treatment and time is not available, the

	STATISTICAL ANALYSIS PLAN, Version Final 2.0
Protocol Number: ASN002AD-201 V3.0	Sponsor: Asana BioSciences, LLC

assessment will be considered as baseline, except for adverse events (AEs) and medications starting on the first study treatment dose date which will be considered post-baseline.

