 Pruritus NRS, emollient use, time of study products administration, and fasting conditions will be recorded daily for 12 weeks in a subject diary. Pruritus NRS and emollient use will be recorded daily in a diary up to Week 16 visit for subjects not entering in the OLE study. Compliance to diary entry, including emollient use, will be verified by the site at every visit.

 Optional, only for a subset of approximately 68 subjects who consent. Photographs should be performed prior to drug administration and biopsy collection (for subjects consenting to biopsies).

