## 5 STUDY POPULATION

### 5.1 Inclusion Criteria

In order to be eligible to participate in this study, a subject must meet all of the following criteria at the screening and Day 1 visits, unless specified otherwise:

1. Male or female subject, aged 18 to 75 years, inclusive, at the time of consent.
2. Subject has clinically confirmed diagnosis of active atopic dermatitis, according to Hanifin and Rajka criteria ([Appendix A](#)).
3. Subject has at least a 6-month history of atopic dermatitis and had no significant flares in atopic dermatitis for at least 4 weeks before screening (information obtained from medical chart or subject's physician, or directly from the subject).
4. Subject has an EASI score  $\geq 16$  at Day 1.
5. Subject has moderate to severe atopic dermatitis at Day 1, as defined by an IGA  $\geq 3$ .
6. Subject has atopic dermatitis covering  $\geq 10\%$  of the BSA on Day 1.
7. Subject has a body mass index (BMI)  $\leq 38 \text{ kg/m}^2$ .
8. Subject has a history of inadequate response to topical corticosteroids or calcineurin inhibitors as treatment for AD within 1 year before the screening visit (information obtained from medical chart or subject history).
9. Subject has been using an emollient (except those containing urea) either once daily or twice daily for at least 1 week prior to Day 1 and agrees to continue using that same emollient, daily and at the same frequency, throughout the study. Note: On the day of scheduled visits, subjects cannot apply emollient before their scheduled visit time.
10. For women of childbearing potential involved in any sexual intercourse that could lead to pregnancy: the subject must agree to use a highly effective contraceptive method from at least 4 weeks before Day 1 until at least 4 weeks after the last study product administration. Highly effective contraceptive methods include hormonal contraceptives (combined oral contraceptive, patch, vaginal ring, injectable, or implant), intrauterine devices or intrauterine systems, vasectomized partner(s), tubal ligation, or double barrier methods of contraception (barrier methods include male condom, female condom, cervical cap, diaphragm, and contraceptive sponge) in conjunction with spermicide.

Note: Subjects must have been on a stable dose of hormonal contraceptives for at least 4 weeks before Day 1.

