5.4 Windowing Conventions

Statistical Windows have been proposed for the efficacy endpoints of this study:

	D1 (Baseline)	W2	W4	W8	W12	W16
Day	1	14	28	56	84	112
Statistical Window	Latest pre-dose measurement	[D1 post dose (i.e. Day 2); day 20]	[Day 21 – Day 34]	[Day 35 – D62]	[D63-D87]	[D88-End of study]

If there is more than one assessment for a given timepoint and analysis visit, the assessment closest to the target day will be considered. If there is more than one assessment with the same target date, then the scheduled assessment result will be considered.

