6.6 Examination of Subgroups

The effect of EASI score at baseline (disease severity) on the treatment effect will be examined for the change-from-baseline EASI, %change-from-baseline EASI, and % subjects with at least a 50%, 75% and 90% reduction in EASI, % subjects achieving at least a 2-grade reduction from baseline to clear (0) or almost clear (1) in IGA, % subjects achieving at least a 2-grade reduction from baseline in IGA.

The change and percent change from baseline in single daily timepoint pruritus NRS at Week 1 (Day 2 up to Day 7) and the change and percent change from baseline in weekly average of the peak daily pruritus NRS at Weeks 1, 2, 4, 8, and 12 as well as the % subjects achieving at least a 4-point reduction from baseline in weekly average of the peak daily pruritus NRS at Weeks 1, 2, 4, 8, and 12 will be presented in the subgroup of subjects with baseline NRS ≥ 4 .

Moreover, inferential statistical analysis will be done at Week 12 for change-from-baseline and %change-from-baseline EASI. Details on the inferential statistical analysis are presented under section 12.1 Primary Efficacy Endpoint.

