Subjective items include loss of sleep and the intensity of pruritus. These are evaluated by having the subjects indicate on a 10.0-cm (0.0 – 10.0) visual analog scale (VAS) the point corresponding to the average value for the last 3 days/nights. The combined maximum score of these two is 20.0.

The sum of the measures above represents the SCORAD, which can vary from 0 to 103. If the subjective scores of pruritus and loss of sleep are excluded, the SCORAD becomes objective SCORAD (score range 0.0-83.0). The score will be set to missing in case of at least one missing value.

SCORAD will be assessed as

[figure not shown]
	STATISTICAL ANALYSIS PLAN, Version Final 2.0
Protocol Number: ASN002AD-201 V3.0	Sponsor: Asana BioSciences, LLC

- the change from baseline in total SCORAD score, sleep and pruritus sub-scores at Weeks 2, 4, 8, and 12.
- The percent change from baseline in total SCORAD score, sleep and pruritus sub-scores at Weeks 2, 4, 8, and 12.

Pruritus Numeric Rating Scale (NRS):

The intensity of pruritus will be recorded for the entire duration of the treatment (daily) using a numeric rating scale (NRS). This will be evaluated by asking subjects to assign a numerical score representing the worst intensity over the last 24 hours of their symptoms on a scale from 0 to 10, with 0 indicating no symptoms and 10 indicating the worst imaginable symptoms. The pruritus NRS is presented in Figure 2. Assessments within 7 days prior to each of the Week 2, 4, 8, and 12 visits, and on Days 2 to 7 of the Week 1 visit, will be used for the calculation of the weekly average of pruritus NRS.

Figure 2: Pruritus Numeric Rating Scale

The pruritus numeric rating scale will be assessed as:

- Change and percent change from baseline in single daily timepoint NRS at Week 1 (i.e. Day 2, Day 3, up to Day 7).
- Change and percent change from baseline in weekly average of the peak daily pruritus NRS at Weeks 1, 2, 4, 8, and 12.
- Proportion of subjects achieving at least a 4-point reduction from baseline in weekly average of the peak daily pruritus NRS at Weeks 1, 2, 4, 8, and 12.

	STATISTICAL ANALYSIS PLAN, Version Final 2.0
Protocol Number: ASN002AD-201 V3.0	Sponsor: Asana BioSciences, LLC

- Time to a 4-point reduction from baseline in weekly average of the peak daily pruritus NRS.

5D-Pruritus Scale:

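### Weekly-average pruritus NRS endpoints are measured against a one-day baseline, which costs precision, mainly on the 4-point response and the time to that response

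*SAP*

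**What the plan says.** The general rule in SAP 5.2 opens with "Unless otherwise specified" and then states that "baseline value will be defined as the last nonmissing assessment prior to or on the first study treatment dose". The efficacy window table in SAP 5.4 agrees, giving the baseline column as "Latest pre-dose measurement". Neither document sets out a different baseline for the pruritus NRS.

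For the scores after baseline, SAP 12.2 builds the weekly average from "Assessments within 7 days prior to each of the Week 2, 4, 8, and 12 visits, and on Days 2 to 7" of Week 1. That is up to 7 scores at Weeks 2, 4, 8 and 12, and 6 at Week 1. No pre-treatment week is listed.

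On collection, the schedules in both documents show no NRS at screening and a first NRS on Day 1. Footnote 14 of protocol Table 1 says that diary items including the NRS "will be recorded daily for 12 weeks in a subject diary". Protocol 7.1.5 ties recording to the treatment period and has the score entered before dosing.

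On analysis, SAP 12.2 adds baseline score as a covariate to the NRS change and percent-change models. The 4-point response is tested by CMH stratified by EASI severity only. Time to a 4-point reduction uses Kaplan-Meier. SAP 6.6 adds that NRS results "will be presented in the subgroup of subjects with baseline NRS" of 4 or more. SAP 6.5 makes all secondary p-values nominal.

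**The concern.** Four sets of results subtract a 6- or 7-day mean from one day's worst-itch score: change, percent change, the 4-point response and the time to that response. A single day carries the full day-to-day variation; a weekly mean carries only part of it. A chance high score on Day 1 makes a 4-point fall easier to reach, and a chance score below 4 makes it impossible. In percent change the same score is also the denominator.

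At stake are the sensitivity of the itch responder comparison and the meaning of the reported response rates. The responder and time-to-response analyses include no baseline NRS term that could absorb the noise.

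**Working it through.** **Inputs.** From the documents: a one-score baseline (SAP 5.2, 5.4), a 7-day mean after baseline (SAP 12.2), 46 evaluable subjects per group (SAP 5.1) and two-sided 0.05 (SAP 5.6). The documents state no NRS standard deviation, response rate or power, so there is no plan figure to reproduce. The remaining inputs are assumptions, in two sets:
- Set A: mean NRS 7.2, between-subject SD 1.6, mean reduction 1.6 (placebo) and 3.2 (active), SD of individual change 1.9.
- Set B: mean NRS 7.3, between-subject SD 1.5, mean reduction 1.5 and 3.5, SD of individual change 2.2.

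Both use whole-number daily scores from 0 to 10, daily within-subject SD σ of 1 to 2, and lag-1 correlation ρ from 0 to 0.6 (set B was run at 0 and 0.5).

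**Step 1: day-to-day error in the change score.** Let v be the variance of a 7-day mean in units of σ².
- Independent days: v = 1/7 = 0.143. One-day baseline: 1 + 0.143 = 1.143. Seven-day baseline: 2 × 0.143 = 0.286. Ratio 4.0.
- ρ = 0.5: v = [7 + 2 × Σ(7−k) × 0.5^k, k = 1 to 6]/49 = (7 + 2 × 5.016)/49 = 0.348. One-day: 1.348. Seven-day: 0.695. Ratio 1.9.

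This is only the day-to-day part of the variance. True differences between subjects in response are the same under either baseline.

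**Step 2: mean change.** Day 1 is scored before dosing and no eligibility criterion uses the NRS, so noise in that score has the same distribution in every arm. In the set B simulation the mean change under the two baselines agreed within 0.01.

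**Step 3: change models with baseline covariate.** In set B the residual SD on placebo goes from 2.10 to 2.21 at σ = 1, ρ = 0 (2.21/2.10 = 1.05), and from 2.11 to 2.28 at σ = 2, ρ = 0 (1.08). Across both sets the increase is roughly 3-11%.

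**Step 4: 4-point response.** Set B, one-day baseline / 7-day baseline, in percent. Each difference is active minus placebo.

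| σ | ρ | Placebo | Active | Difference | Shrinkage (points) | Classified differently: placebo, active |
|---|---|---|---|---|---|---|
| 1.0 | 0 | 15.3 / 13.1 | 41.3 / 40.2 | 26.0 / 27.1 | 1.1 | 7.4, 12.7 |
| 1.0 | 0.5 | 15.8 / 14.1 | 41.7 / 40.6 | 25.9 / 26.5 | 0.6 | 7.0, 11.8 |
| 1.5 | 0 | 16.9 / 13.2 | 40.8 / 39.0 | 23.9 / 25.8 | 1.9 | 10.1, 16.9 |
| 1.5 | 0.5 | 17.6 / 14.9 | 41.0 / 39.7 | 23.4 / 24.8 | 1.4 | 9.6, 15.4 |
| 2.0 | 0 | 18.3 / 12.9 | 40.0 / 37.2 | 21.7 / 24.3 | 2.6 | 12.4, 20.2 |
| 2.0 | 0.5 | 19.4 / 15.8 | 40.6 / 38.7 | 21.2 / 22.9 | 1.7 | 11.7, 17.9 |

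Under set A, response rises by about 2-7 points on placebo and 2-5 on active, and the between-arm difference shrinks by about 0.5-1.5 points. Over both sets, the two baselines disagree for about 7-13% of placebo and 12-21% of active subjects.

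**Step 5: what this does to the responder comparison.** Unadjusted two-proportion normal approximation, 46 per arm, set B at σ = 1.5, ρ = 0:
- One-day: pooled rate (0.169 + 0.408)/2 = 0.2885; null SE = √(2 × 0.2885 × 0.7115/46) = 0.0945; alternative SE = √[(0.169 × 0.831 + 0.408 × 0.592)/46] = 0.0911; z = (0.239 − 1.96 × 0.0945)/0.0911 = 0.59; power about 72%.
- Seven-day: pooled rate 0.261; null SE 0.0916; alternative SE 0.0875; z = (0.258 − 1.96 × 0.0916)/0.0875 = 0.90; power about 81%.

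Over the six rows, power is 60.5-79.9% with one day and 70.3-84.7% with seven, a loss of about 3 to 14 points. Part comes from the smaller difference and part from the larger binomial variance at higher response rates.

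**The case against.** **The baseline may not be a single score.** The endpoint wording could be taken to imply a weekly-average baseline, SAP 5.2 allows exceptions, the table layouts are in a separate document, and diary verification is ticked at Day 1, which may hint at earlier entries. But no exception is written for the NRS, the NRS and diary rows start on Day 1, and even with earlier entries SAP 5.2 would use only the last one. The point limits confidence about which data exist. It does not supply a definition.

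**The change models are already protected.** Largely true. The baseline covariate limits the loss, and the increase in unadjusted change variance is not the relevant measure for those analyses. The single-day endpoint for Days 2 to 7 compares one day with one day, so it has no mismatch.

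**The stakes are low.** Also true in part. These are secondary endpoints with nominal p-values, and the sample size rests on EASI and IGA.

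**Classified differently does not mean misclassified.** A reader might infer that 12-21% of active subjects receive a wrong responder status. That is not shown: a 7-day baseline is imperfect too. Against long-run status in set B with σ of 1 to 2, disagreement on active is 14.8-25.4% with one day and 7.9-20.2% with seven. The excess, scenario by scenario, is about 4-10 points on active and 3-7 on placebo.

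**The subgroup with baseline NRS of 4 or more.** Selecting on one noisy score does cause regression to the mean in all arms, but under these assumptions the cut removes only about 2-8% of subjects. The effect is minor.

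**Conclusion.** The point stands as a loss of precision on secondary endpoints. As written, the SAP compares one pre-dose daily score with a 6- or 7-day mean. The main cost falls on the 4-point response and the time to it. Response rates rise by about 2-7 points on placebo and 1-5 on active, and the between-arm difference shrinks by about 0.5-1.5 points (set A) or 0.6-2.6 (set B). The change models lose roughly 3-11% in residual SD.

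Every size rests on assumed NRS variability and effects. That one day is noisier than a 7-day mean does not depend on the values chosen, as long as daily scores are not perfectly correlated.

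A reader might go further and infer a biased treatment effect on itch or a threat to the trial's main conclusion. The documents do not support either. Randomisation and pre-dose scoring leave the between-arm difference in mean change unbiased, and the primary EASI analysis does not use the NRS. Grade it as an inexpensive improvement.

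**What to change.** **In the protocol:** start the NRS diary at least 7 days before Day 1. This fits within the 30-day screening period and the period of emollient use that inclusion criterion 9 already requires "for at least 1 week prior to Day 1".

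**In SAP 5.2 and 12.2:** define NRS baseline as the mean of the daily scores in the 7 days up to the Day 1 pre-dose entry, with a stated minimum number of entries. Use it for all weekly-average endpoints and for the subgroup with baseline NRS of 4 or more. Keep the one-day baseline for the single-day Week 1 endpoint.

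**Cost:** the diary is handed out at screening and each subject makes seven more entries; no extra visit or staff. A SAP sentence alone is not enough, because it cannot create scores that were never collected.

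**If scores before Day 1 can no longer be collected:** use any that exist, say explicitly in the SAP that baseline is otherwise the single Day 1 score, and add a 4-point responder analysis adjusted for baseline NRS, for example logistic regression with treatment, severity stratum and baseline NRS. This costs one additional model.

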5.3 Reference Start Date and Analysis Day

Analysis day will be calculated from the first study treatment date and will be used to show start/end day of assessments or events.

In the situation where the assessment/event date is partial or missing, analysis day will be missing.

5.4 Windowing Conventions

Statistical Windows have been proposed for the efficacy endpoints of this study:

	D1 (Baseline)	W2	W4	W8	W12	W16
Day	1	14	28	56	84	112
Statistical Window	Latest pre-dose measurement	[D1 post dose (i.e. Day 2); day 20]	[Day 21 – Day 34]	[Day 35 – D62]	[D63-D87]	[D88-End of study]

If there is more than one assessment for a given timepoint and analysis visit, the assessment closest to the target day will be considered. If there is more than one assessment with the same target date, then the scheduled assessment result will be considered.

5.5 Descriptive Statistics

All continuous variables will be summarized by presenting the number of subjects, mean, standard deviation, median, minimum, and maximum. Categorical variables will be presented as frequencies and percentages. Summary tables will be presented by treatment and visit, when applicable.

Change from baseline will be calculated as:

Assessment value at post-baseline visit X – baseline value.

Percent change from baseline will be calculated as:

(Assessment value at post-baseline visit X – baseline value) / baseline value * 100.

	STATISTICAL ANALYSIS PLAN, Version Final 2.0
Protocol Number: ASN002AD-201 V3.0	Sponsor: Asana BioSciences, LLC

5.6 Statistical Tests

Unless otherwise specified, all statistical tests will be two-sided and will be performed with a significant level of 0.05. Confidence intervals (CIs) will be two-sided with 95% coverage.

5.7 Handling of Retests, Unscheduled Visits, and Early Termination Data

When retests measurements are done, the retest measurement will be considered for the summary analysis. All data from retest visits will be listed.

For safety data, unscheduled measurements will not be summarized in by-visit summary tables or figures. However, data from unscheduled visits will be listed. Early Termination (ET) visit assessments will be summarized as a separate visit in by-visit outputs.

For efficacy data, unscheduled measurements and ET visit assessments will be re-mapped according to the windowing conventions in section 5.4.

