#### **4.4.1 Interruption criteria**

A subject who meets either of the below criteria will have the study drug interrupted until laboratory retesting is performed and/or event resolution.

- neutrophils  $> 0.5 \times 10^3 / \mu\text{L}$  but  $< 1 \times 10^3 / \mu\text{L}$ ;
- platelet count  $> 50 \times 10^3 / \mu\text{L}$  but  $< 100 \times 10^3 / \mu\text{L}$ ;
- lymphocytes  $< 0.5 \times 10^3 / \mu\text{L}$  but  $> 0.2 \times 10^3 / \mu\text{L}$ ;
- CPK  $> 10 \times \text{ULN}$ ;
- an infection requiring IV treatment with antiviral, antibiotic, antiprotozoal, antiparasite or requiring oral medications of those longer than 2 weeks;
- AST/ALT  $> 5 \times \text{ULN}^*$ .

\*Decision to restart the medication following any laboratory abnormality described above will be made in consultation with the study sponsor and medical monitor.

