## 5.4 Screen Failures

Screen failures are defined as individuals who consent to participate in the clinical trial, but are not subsequently randomly assigned to the study products. A minimal set of screen failure information is required to ensure transparent reporting of screen failure subjects, to meet the Consolidated Standards of Reporting Trials (CONSORT) publishing requirements, and to respond to queries from regulatory authorities. Minimal information includes demography, screen failure details, eligibility criteria, and any SAEs.

Individuals who do not meet the criteria for participation in this trial (screen failure) may be rescreened once, if deemed acceptable by the investigator. Rescreened subjects should be assigned a different subject number than the initial screening. All procedures planned at the screening visit, including signature of a new consent form, will be performed.

Subjects who do not qualify to participate in the study due to a screening laboratory value abnormality can repeat the test once within the original screening time window without resulting in screen failure, if the investigator believes there is a reasonable possibility that the subject would be eligible if re-tested.

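### The retest rule in SAP 5.7 is unrestricted and SAP 13.2 has no worst-post-baseline summary, so transient or off-schedule laboratory abnormalities can be missing from the per-arm laboratory tables

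*SAP*

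**What the plan says.** SAP 5.7 sets three rules that matter for laboratory data.

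- Retests: "When retests measurements are done, the retest measurement will be considered for the summary analysis". No condition is placed on timing, reason or sample validity. The next sentence adds "All data from retest visits will be listed".
- Unscheduled safety values: "unscheduled measurements will not be summarized in by-visit summary tables or figures". They are listed only.
- Early termination (ET) values appear in by-visit outputs as their own visit.

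The section treats retest visits and unscheduled visits as different things but defines neither. Visit windows do not settle the matter, because SAP 5.4 opens with "Statistical Windows have been proposed for the efficacy endpoints of this study" and gives none for safety data.

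SAP 13.2 plans descriptive statistics, change from baseline at each post-baseline assessment, and shift tables from baseline to each post-baseline visit and timepoint. The shift tables are restricted to subjects who have both a baseline result and one at the visit concerned. SAP 13.2 also plans full listings and separate listings of abnormal results. Neither SAP 13.2 nor Protocol 8.3.3 plans a worst-post-baseline summary.

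The protocol foresees two kinds of laboratory repeat. At screening, a subject with an abnormal value "can repeat the test once within the original screening time window" (Protocol 5.4). On treatment, Protocol 4.4.1 says "A subject who meets either of the below criteria will have the study drug interrupted until laboratory retesting is performed and/or event resolution".

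**The concern.** A retest is usually ordered because a value was abnormal. If the retest then replaces that value, selection for replacement depends on the result, and the replacement may come from a period when study drug was held. A transient drug effect is what such a rule would remove from the by-visit statistics and shift tables.

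Separately, an abnormality that first appears at an unscheduled draw has no row in any laboratory summary, because there is neither a by-visit place for it nor a worst-value table to collect it.

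Change in safety laboratory tests is a named secondary safety endpoint (SAP 2), and the SAP 13.2 tables are its aggregate comparison across arms. A reader who wanted the missing cases by arm would have to count them by hand from listings or rely on adverse event tables, which depend on a change having been judged significant.

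**Working it through.** There is no figure in the plan to reproduce; the check is which values reach which table.

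**Two readings of SAP 5.7.** Because a retest is not defined, a repeat drawn after a scheduled visit can be handled in two ways.

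- Reading A, the literal one: the retest takes the place of the scheduled value in the summary.
- Reading B: the repeat is classed as unscheduled, so it is left out and the scheduled value stays.

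Tracing cases through SAP 5.7 and 13.2, for one subject with a normal baseline and one parameter:

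| Case | Counted as a shift to abnormal, reading A | Counted, reading B |
|---|---|---|
| Week 4 abnormal, retest normal | No | Yes |
| Week 4 abnormal, retest abnormal | Yes | Yes |
| Scheduled values normal, unscheduled value abnormal | No | No |
| Abnormal at ET visit | Yes, ET row | Yes, ET row |

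Row 1 is where the readings differ. Rows 1 and 2 show the direction under reading A: for the parameter that triggered the retest, the shift count is unchanged or falls by one, and it cannot rise. The by-visit minimum and maximum, which are among the SAP 5.5 statistics ("number of subjects, mean, standard deviation, median, minimum, and maximum"), can move either way, since a retest may be more extreme than the value it replaces. Row 3 does not depend on the reading.

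**Is the unrestricted rule needed for baseline?** No. SAP 5.2 already takes the last non-missing pre-dose value and includes unscheduled assessments, so a screening repeat can serve as baseline without SAP 5.7.

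**Where it can arise.** Protocol Table 1 has four post-dose visits in the treatment period (Weeks 2, 4, 8, 12). Laboratory tests are scheduled at two of them (Weeks 4 and 12), and again at follow-up/ET. With the SAP 5.4 target days, the interval between the two on-treatment tests is 84 − 28 = 56 days, during which only an unscheduled draw or an ET visit can show an abnormality. No drug is given at the Week 12 visit (Table 1, footnote 13), so a Protocol 4.4.1 retest of a scheduled value concerns Week 4. The SAP rule itself covers a retest after any visit.

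**Weight of one uncounted subject in an arm's proportion.**

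- Planned enrolment, 55 per group (SAP 5.1): 1/55 = 1.82 points.
- Planned minimum, 46 per group (SAP 5.1): 1/46 = 2.17 points.
- 160 evaluable over 4 arms = 40 per group: 1/40 = 2.50 points.

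The last two denominators come from efficacy planning. Laboratory tables use the safety population with a baseline and a visit result, so these figures only illustrate scale.

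**The case against.** The strongest reply has five parts.

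- **Nothing is lost.** Retest and unscheduled values are all listed, and abnormal results are listed separately, ordered by treatment group (SAP 13.2, Appendix 1). This stands; the gap is confined to aggregate tables.
- **Adverse event tables carry the important cases by arm.** SAP 13.1 names neutropenia, lymphopenia, eosinopenia, CPK elevation and anemia for per-arm summary. These cover three of the five laboratory triggers in Protocol 4.4.1 (neutrophils, lymphocytes, CPK). Events leading to treatment interruption are also summarised, and an unblinded DSMB reviews safety by arm at least three times. This largely stands for values at the Protocol 4.4.1 level. It is not complete: platelets and AST/ALT are not among the named events and would appear only in the general tables. Reporting rests on a change being judged significant (Protocol 7.3.4), and Protocol 7.6.5 prefers the underlying diagnosis to the abnormal test.
- **Reading B is the more natural one**, since an on-treatment repeat would usually be an extra visit. That is possible, but the SAP does not say so, and its retest sentence carries no exception. Reading B also leaves off-schedule findings uncounted.
- **No document promises a worst-value table.** True: its absence contradicts nothing in the plan, and the table layouts are in a separate document (SAP 5). It is proposed because the planned rules leave some abnormalities with no place in a per-arm laboratory table.
- **The one-way effect is not general.** Correct: it applies to the triggering parameter. If a whole repeat panel replaced the earlier panel, other parameters could turn abnormal, and the SAP does not say whether replacement is by parameter or by panel.

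**Conclusion.** The concern holds, as a minor point about aggregate laboratory reporting. Under the literal reading, replacement can only leave unchanged or lower the shift-to-abnormal count for the parameter that triggered the retest. Under either reading, an abnormality first found at an unscheduled draw is absent from every planned laboratory summary table.

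The overall size is unknown, because no abnormality, retest or unscheduled-draw rates are given. About two percentage points of an arm per affected subject is the scale. Under reading B, replacement removes no one and only off-schedule findings are uncounted. The conclusion assumes that being considered for the summary means being used in place of the earlier value, since nothing says that both are summarised. Efficacy results are unaffected.

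**What to change.** In SAP 5.7:

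- define a retest and distinguish it from an unscheduled measurement;
- keep the valid on-treatment value at its scheduled visit in by-visit safety summaries;
- allow a retest to replace a value only for pre-dose repeats or samples documented as invalid.

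In SAP 13.2, add for each arm a shift table from baseline to the worst post-baseline value, drawing on scheduled, unscheduled, retest and ET results. Show the number of post-baseline draws per arm beside it.

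The cost is a few lines of text and one more shift table per laboratory panel. No new data are needed. The downsides are more output and laboratory summaries that may look slightly less favourable. A worst-value table also gives an arm with more unscheduled draws more chances of an abnormal result, which is why the draw counts should be shown.
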